# 5.5. Selection of patients where chemotherapy and/or anti-HER-2 therapy is not indicated at the time of trial entry

The study is designed to recruit patients who would not normally receive neoadjuvant or adjuvant chemotherapy since this is the context in which NET is recommended as an option within NICE guidance. Patient consultation confirmed that patients who knew they required chemotherapy would prefer to have NAC or immediate primary surgery and adjuvant chemotherapy, as chemotherapy following NET would significantly extend the duration of active treatment.

The recommendation for chemotherapy in early breast cancer is based on evaluation of risk and benefit. In clinically node negative patients with intermediate risk ER+/HER2-tumours baseline molecular profiling is currently available (59) and can be performed on the diagnostic core biopsy if this will inform decision making. If the oncological decision is that chemotherapy is not recommended, the patient can be approached for participation in the EndoNET trial. In patients in whom it was felt chemotherapy would not be given due to co-morbidity, patient preference or marginal benefit, then the patient can also be offered study participation.

Despite best efforts however, it is anticipated that there will be small numbers of cases where it is felt at baseline that chemotherapy or anti-HER2 therapy was not indicated, but at a later stage or following surgery the disease was found to be more extensive than anticipated; for example, patient with negative lymph nodes at diagnosis based on ultrasound assessment (+/- core biopsy or fine needle aspiration cytology) but with histologically positive lymph nodes at surgery. In these cases, adjuvant chemotherapy or anti-HER2 therapy should be given as per usual centre protocol. The control arm will follow usual clinical pathways after surgery. In the NET arm this will be after 6 months of NET and subsequent surgery. This possibility will be mentioned in the study literature for those who would opt for and be fit for chemotherapy should there be unexpectedly felt to be a benefit following surgery. If during the course of the study molecular profiling guidelines change, for example extending the indication for molecular profiling to node positive patients this will be permitted as part of a pragmatic "real-world" study design.

Patients with ER+ tumours where the HER-2 result is unknown or outstanding may be entered into the trial where this is felt by the treating clinical care team that chemotherapy/anti-HER-2 therapy would not be given, regardless of the result. If following trial entry and prior to surgery it becomes apparent that the tumour is HER-2 positive, participants will remain on the trial and within trial follow up and receive appropriate treatment.

#### 5.6. The need for the EndoNET trial

During the COVID-19 pandemic, and its multiple waves, large numbers of patients within the UK and worldwide were placed on "bridging" NET until theatre capacity became available, despite lack of level 1

© Copyright: The University of Oxford and Oxford University Hospitals NHS Foundation Trust 2022 Page 27 of 84

evidence. It is therefore important going forward to understand the significance, impact and effectiveness of a NET strategy, which continues to be used post-pandemic in secondary care UK hospitals.

If NET is shown to increase BCS rates (reducing mastectomy rates) and reduce burden of surgery (smaller volume resections, reduced re-excision rates and reduced axillary treatment) there would be significant benefit to both patients and to the NHS, including reduced quantity and extent of surgery, quicker recovery and progression to further adjuvant treatments, improved cosmesis, satisfaction, body image, self-esteem, sexuality and reduced anxiety and depression (8). These patient and health economic benefits are commensurate with the objectives of the national "getting it right first time" (GiRFT) initiative (60). The detrimental effects of mastectomy to HRQoL and body image persist regardless of age (20, 23, 24). Benefits to women of BCS include better HRQoL and a reduction in requirement for post-mastectomy reconstruction and its complications. For those treated by BCS, the benefits of NET potentially include reduction in excision volumes, fewer patients requiring for more complex BCS techniques and reduction in re-excision rates. Since ET is widely given and of low toxicity, benefit would be seen across the age spectrum. Improving cancer outcomes in the elderly is important (61) and as comorbidity and age increases, mastectomy is more likely, whilst reconstruction and chemotherapy (including as a neoadjuvant/downstaging option) is less frequently utilised (4).

Our trial design addresses the question defined in the NIHR brief which was also highlighted as important by NICE (26). The NICE systematic review compared NET to no NET (i.e. primary surgery followed by adjuvant treatment), or to NAC. The consensus amongst clinicians and patients was that the comparison of greatest clinical need was of NET compared to no NET since the majority (>70%) of post-menopausal women with ER+ breast cancer will not receive chemotherapy (4). Furthermore, despite advantages of NAC, a meta-analysis has failed to show benefit in terms of improvements in surgical outcomes (62), and a previous UK trial comparing NAC to NET closed due to failure to recruit (63). Our comparison of NET to no NET allows inclusion of patients less often included in clinical trials (e.g. older patients with comorbidities) and provides a downstaging option for those who would not be treated with chemotherapy. Since all ER+ patients will usually receive adjuvant ET, it will allow us to apply the findings to a very wide group who would not benefit from NAC, and therefore would otherwise not have an option to have their tumour size reduced to facilitate less extensive surgery. A non-NET control arm also enables absolute quantification of the magnitude of effect on endpoints such as tumour shrinkage and breast conservation rates, as opposed to a relative quantification and would establish NET AI monotherapy as a safe comparator in future clinical trials of current and novel ET combinations, several of which are already established in the treatment of advanced disease.

## 5.7. The need for the Nested Qualitative Study (NQS)

The nested qualitative study (NQS) is a sub-study embedded within the main trial. The NQS, through the use of qualitative methods, will explore the experiences of participants in the trial and their subsequent treatments of breast cancer. This will provide context to the HRQoL data of women taking part in the trial and will guide and assist the analysis and interpretation of the HRQoL findings and outcomes.

EndoNET\_Protocol\_V4.0\_21Aug2024

© Copyright: The University of Oxford and Oxford University Hospitals NHS Foundation Trust 2022 Page 28 of 84 It is important to implement the sub-study to ensure that questions that cannot be answered by the trial data alone, such as a lack of treatment effect, can be understood. Further information can be found in Section 9.15.

#### 5.8. The need for Trans-EndoNET

Trans-EndoNET aims to characterise the relationship between patient insulin metabolism and tumour response to endocrine therapy in early breast cancer. Increased insulin levels are associated with higher breast cancer incidence and mortality. This will involve the collection of a fasted blood sample at baseline and use of the existing tissue samples collected for the main study. Trans-EndoNET will be conducted in a sub-set of participants at a later stage of the trial.

## 6. OBJECTIVES AND OUTCOME MEASURES

#### **6.1 HYPOTHESIS:**

Neoadjuvant endocrine therapy (NET) reduces breast cancer size prior to surgery, reducing surgical burden resulting in a higher proportion of patients treated with breast conservation surgery (BCS).

RESEARCH QUESTION: In post-menopausal women with ≥15mm, strongly ER+, invasive breast cancer, where chemotherapy or anti-HER-2 therapy is not planned, does NET increase the proportion of patients who have BCS by 15 months post-randomisation?

	Objectives	Outcome Measures	Timepoints
Primary	The overall aim is to evaluate whether 6 (+/- 1) months of NET reduces surgical burden resulting in a higher proportion of breast conservation in post- menopausal women with ≥15mm, strongly ER+ breast cancer who are not planned or have not started chemotherapy or anti- HER-2 therapy 	Proportion of patients who have breast conservation (surgery)	15 months post- randomisation
Secondary	
 
To evaluate whether 6 months of NET results in better HRQoL over 15 months
 
	
 
Difference in global HRQoL (as measured by FACT-B)
 
	
 
Baseline, 6 weeks or post-operative, 5 and 15 months post- randomisation
 

#### 6.2 Primary and secondary outcome measures

2	. To evaluate tumour response rates following NET 	2.	Response rates according to RECIST (USS, clinical, relative to baseline); MRI where used as part of local unit centre policy	2.	2-4 weeks, 3 and 5 months post- randomisation (NET arm)
3	
 
To compare invasive tumour size, histological grade and lymph node status (including number of involved nodes) in both arms
 
	3.	Tumour size, histological grade and lymph node status pre-surgery and final histology post-surgery	3.	Pre and post- operative
4		4.	Patient reported outcomes as measured by FACT-B (with ES and +4), Breast-Q, Hopwood Body Image Scale and EQ-5D-5L	4.	Baseline, 6 weeks or post-operative, 5, 7, and 15 months post- randomisation 
5		5.	Pre-operative Endocrine Prognostic Index (PEPI) score	5.	Baseline sample, 2-4 week sample and post- operative sample
6	To compare post-surgical complications and AI side effects in both arms 	6.	Post-surgical complications, side effects; delays to commencement of subsequent treatment	6.	2-4 and 6 weeks, 3 months, 5, 7, 12 and 15 months post- randomisation
7		7.	Treatment Compliance and rates of cross-over	7.	2-4 weeks, 5 months and 15 months post- randomisation.
8	. To evaluate the prognostic significance of Ki67 	8.	Ki67 % in tumour cells, % reduction in Ki67 from baseline to biopsy or surgery	8.	Baseline (both arms) and after 2- 4 weeks of AI (in both arms) and at surgery (in comparator arm);

9. To assess the surgical and locoregional management of the breast 	9. Rates of re-excision and further surgery after BCS; specimen weight after BCS; requirement for advanced BCS (therapeutic mammoplasty and local perforator flaps), rate of reconstruction	9. Baseline, post- operative, 15 months post- randomisation
10. To assess the surgical and locoregional management of the axilla 	postmastectomy, breast radiotherapy 10. Rates of sentinel node biopsy, axillary clearance, axillary radiotherapy	10. Baseline, post- operative, 15 months post- randomisation
11. To compare rates of local and distant recurrence 	11. Rates of local and distant recurrence	
 
11. 15 months post- randomisation, and periodically for long term follow up 
 


 
To compare breast cancer specific survival in both arms 
 
	12. Breast cancer specific and overall survival	12. 15 months post- randomisation and periodically for long term follow up 
13. To assess the cost- effectiveness of implementing NET followed by surgery and adjuvant ET compared with the current practice of surgery followed by adjuvant ET for reduction in mastectomy (Health Care Use Questionnaire) 	13. Resource utilisation, cost and cost- effectiveness of implementing NET followed by surgery and adjuvant ET compared with the current practice.	13. Baseline, 6 weeks, 7 months and 15 months post randomisation
14. To compare accuracy of Ultrasound	14. Accuracy of USS (and MRI where available) to	14. Up to 15 months post- randomisation

			ſ	
	(USS) and		determine	
	where		conversion to BCS	
	available) for			
	assessment			
	initial extent			
	disease	and for		
	detectio	n of		
	tumour			
	response	e, using		
	these tw	0		
	different	t		
	imaging			
	modaliti	es 1		
	15. To comp	are the	15. Number of patients	15. At 15 months.
	requiren	nent for	receiving adjuvant	
	adjuvant	t	chemotherapy in	
	chemoth	nerapy	both arms	
	in both a	arms 		
Exploratory (	Objectives (option	nal sub-st	tudies)	
Integrated re	esearch study	1) To su	pport recruitment processes	In real time, from when
(QuinteT Rec	ruitment	from the outset of the trial, through:		the first site opens to
Intervention	to understand		ith developing patient-facing	recruitment until 12
and address i		information about the study and		months after the last site
	ceruitment			
issues			ed recruitment training for	opens - 36 months of the
		site-staf	т.	recruitment period
		2) To understand recruitment issues		
		-		
		arising in EndoNET in 'real-time',		
		•	: interviews with the trial	
		team an	nd site staff involved in	
		recruitm	nent processes; audio	
		recording of recruitment discussions		
		between site staff and patients;		
			analysis of study	
			entation, and quantitative	
			•	
		analyses	s of screening logs.	
		3) To de	evelop and implement	
			' to support recruitment in	
			ration with the TMG and PPI	
		-	s, based on findings from the	
		above		

Nested qualitative study (NQS). The sub-study aims to explore the experiences of patients during the trial recruitment period, generating an understanding of the acceptability and experiences of NET and subsequent treatments on women's HRQoL from the perspective of patients. This will guide and assist interpretation of HRQoL findings and outcomes.	
 
To explore the experiences of participants in both the intervention and control arms of the trial to:
 
Understand participant experiences, beliefs and expections of NET
 
Generate an understanding of the acceptability of NET
 
Understand participant experiences of subsequent treatment after NET.
 
To understand how these experiences may affect their health- related quality of life, to help understand the FACT-B scores
 
To understand whether these experiences vary with participant characteristics (e.g. age, treatment type) and if so, how?
 
	
 
Post-randomisation prior to NET starting, or as soon as possible after starting pre- surgical endocrine therapy
 
6 months after surgery.
 
Participants in active follow up on the trial may also be interviewed at varying timepoints, for example if they have crossed over to early surgery.
 

---	--	--

**Table 2:** Primary and secondary outcomes measures

 Outcomes within objective measured in both the intervention (NET) and control arm.

Outcomes within objective measured in intervention (NET) arm only.

 Breast-Q administered at baseline and 15 months only. EQ-5D-5L administered at baseline, 6 weeks, 7 months and 15 months only. Hopwood BIS administered at baseline, 5 months and 15 months only. FACT-B with ES and +4 administered at baseline, 6 weeks, 5 months and 15 months. Refer to schedule of trial procedures in Section 9.2.

 These are secondary objectives that will be assessed subject to additional funding and/or resource and via submission of an amendment, for example, at 5, 10 and 20 years or more within the EndoNET trial long follow up. Patients will be consented for long term follow-up on EndoNET trial entry.

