Participants in this randomised controlled trial are allocated by chance to one of two arms, which determines their treatment schedule. Endocrine therapy is usually started after surgery. However, all participants in both trial arms will start endocrine therapy (letrozole, anastrozole or exemestane) on joining the trial and prior to surgery. Therefore, they may have the opportunity to start treatment with endocrine therapy before they normally would. If patients start aromatase inhibitor endocrine therapy following their current diagnosis of breast cancer as part of routine care before the trial, this is allowed provided the endocrine therapy was not started more than 14 days prior to trial entry.

Participants in both arms have endocrine therapy for the same total length of time within the trial, but it is the timing of the surgery that differs. The type of surgery all participants will have will be determined by them and their clinical team as part of standard clinical care. Arm 1 will have surgery within 2-4 weeks (up to 8 weeks permitted for trial purposes) of starting their pre-surgical endocrine therapy; arm 2 will receive surgery after 6 months (+/-1 month) of pre-surgical endocrine therapy (neoadjuvant endocrine therapy;

EndoNET\_Protocol\_V4.0\_21Aug2024

© Copyright: The University of Oxford and Oxford University Hospitals NHS Foundation Trust 2022 Page 11 of 84 NET). Participants in Arm 2 will receive an ultrasound (USS) scan at 3 months and 5 months to closely monitor their response to this endocrine therapy prior to their surgery.

Patients with breast cancer, included as part of the study leadership team, and others have been extensively consulted in the trial design. They indicated preserving the breast and overall quality of life as the most important outcomes by which to measure study success.

The trial aims to recruit at least 792 women from at least 30 NHS hospitals across the UK. Participants in both arms will have their surgical treatments recorded and will complete quality of life questionnaires at intervals during their 15-month participation in the study. The results will be published in medical journals and presented at international conferences and updates of study progress will be available on the website and by study newsletter.

As part of this research, we are also running sub-studies to which patient participation is optional:

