# 7. TRIAL DESIGN

#### 7.1 Type of trial

This is a prospective, phase III, parallel group, multicentre, superiority randomised controlled trial (RCT).

EndoNET\_Protocol\_V4.0\_21Aug2024

© Copyright: The University of Oxford and Oxford University Hospitals NHS Foundation Trust 2022 Page 33 of 84

We will recruit a maximum of 1,060 (for 90% power) with a minimum of 792 (for 80% power) postmenopausal women with strongly ER+ invasive breast cancer who are not planned or have not started chemotherapy or anti-HER-2 therapy from secondary care UK hospital breast units. They will be randomised 1:1 to undergo 6 (+/- 1) months of NET followed by surgery and adjuvant ET or to surgery within 2-4 weeks (up to 8 weeks permitted for trial purposes) followed by adjuvant ET. Flexibility in the scheduling of a month either side of the target of 6 months in the NET arm and up to 8 weeks in the comparator arm is designed to accommodate the practicalities of the logistics of surgical planning. It was also highlighted an important factor by patients at the PPI meeting and is consistent with levels of pragmatic flexibility. Both arms receive the same treatment modalities (surgery, ET, and radiotherapy where indicated), but the sequencing of surgery will differ, with both arms starting ET at randomisation, with 6 months of the course of ET delivered prior to surgery in the NET arm. The primary outcome measure is the proportion of women who have BCS at 15 months. If aromatase inhibitor endocrine therapy has already been started following the current breast cancer diagnosis as part of routine care prior to joining the trial, then this is permitted, as long as trial entry is within 14 days of starting treatment.

The study duration is 69 months including, 6 months setup, 42 months recruitment, 15 months follow-up and 6 months data analysis and final reporting of results.

[figure not shown]
A formal stop/go review took place on 31st December 2023 to ensure 12 sites opened and 150 participants were randomised. The Funder granted a continuation of recruitment with a second review point in December 2024. Data from the internal pilot will be included in the final analysis.

EndoNET\_Protocol\_V4.0\_21Aug2024

© Copyright: The University of Oxford and Oxford University Hospitals NHS Foundation Trust 2022 Page 34 of 84

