## **11.4.** Reporting complications in relation to surgery

Any complications related directly to breast surgery and not considered related to AI treatment (example: prolonged hospitalisation, infection etc.) will not be part of the safety reporting but will be collected in the relevant trial CRF. These will be assessed using the Clavien-Dindo Classification of surgical complications.

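### Outcome 6 compares post-surgical complications on a clock that starts at randomisation, giving control about 13 to 14.5 months of post-operative time at risk and NET 8 to 10; a crude comparison to month 15 may favour NET

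*Protocol*

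**What the plan says.** Objective 6 in Protocol Section 6.2 is comparative: "To compare post-surgical complications and AI side effects in both arms". Its outcome measure combines three things: "Post-surgical complications, side effects; delays to commencement of subsequent treatment". All three share one set of timepoints, "2-4 and 6 weeks, 3 months, 5, 7, 12 and 15 months", counted from randomisation. The Synopsis (Section 3) gives the same list.

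The timing of surgery differs by design. The Lay Summary (Section 2) states for control that "Arm 1 will have surgery within 2-4 weeks (up to 8 weeks permitted for trial purposes) of starting their pre-surgical endocrine therapy", and for NET that "arm 2 will receive surgery after 6 months (+/-1 month) of pre-surgical endocrine therapy". Section 7.1 confirms the permitted flexibility: "a month either side of the target of 6 months in the NET arm and up to 8 weeks in the comparator arm". Section 9.20 sets funded follow-up at 15 months per participant.

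On surgical complications, Section 11.4 takes them out of safety reporting and puts them on a trial CRF: "These will be assessed using the Clavien-Dindo Classification of surgical complications". It names no post-operative interval. Section 12.2 gives a chi-squared test and a relative risk as the default for binary clinical endpoints, mentions no allowance for time since surgery, and leaves full details to the SAP.

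**The concern.** The natural origin for a complication of surgery is the operation. When the clock starts at randomisation and stops at month 15, the arm operated on first is observed for longer after surgery. Any complication that arises late has more opportunity to be counted in control than in NET, so the imbalance can act in only one direction, in favour of delayed surgery.

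The protocol uses a surgical anchor elsewhere. Outcomes 3, 5, 9 and 10 include a post-operative timepoint, and outcomes 1 and 4 allow a post-operative alternative to week 6. Outcome 6, the one that deals with surgical complications, has none. Section 9.2 also states the aim that assessments should fall at matching stages of care in the two arms where this can be done.

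Outcome 6 is the main comparison of surgical harm. Complications due to surgery alone are outside safety reporting (Section 11.4), and the window for reporting serious adverse events ends at surgery (Section 11.8). With equal true rates, delayed surgery could appear somewhat safer, and a true excess in NET could be partly masked.

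**Working it through.** **Plan's own figure.** The protocol gives no complication rate, timing or power for this outcome, so there is none to reproduce. The total sample sizes of 1060 and 792 (Section 12.3) concern breast conservation and are not affected.

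**Inputs.**
- Visits, Section 6.2: 2-4 weeks, 6 weeks, and 3, 5, 7, 12 and 15 months from randomisation.
- Surgery: control at 2-4 weeks, up to 8; NET at 5 to 7 months (Sections 2 and 7.1).
- End of follow-up: 15 months (Section 9.20).
- One month = 30.4375/7 = 4.348 weeks, so 2, 4 and 8 weeks are 0.46, 0.92 and 1.84 months.
- Surgery is taken as on schedule, with AI started at randomisation. Up to 14 days of earlier AI is allowed, which could bring surgery forward by up to two weeks on the randomisation clock.

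**Step 1: post-operative time = 15 − month of surgery.**

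| Arm | Surgery | Post-operative months | Listed visits after surgery | Surgery to first listed visit |
|---|---|---|---|---|
| Control | 2 weeks | 15 − 0.46 = 14.5 | 6 | 4 weeks |
| Control | 4 weeks | 15 − 0.92 = 14.1 | 6 | 2 weeks |
| Control | 8 weeks | 15 − 1.84 = 13.2 | 5 | 1.2 months |
| NET | 5 months | 10 | 3 | 2 months |
| NET | 6 months | 9 | 3 | 1 month |
| NET | 7 months | 8 | 2 | 5 months |

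At target timing the gap is 14.1 − 9 = 5.1 months. Across the permitted limits it runs from 13.2 − 10 = 3.2 to 14.5 − 8 = 6.5 months.

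**Step 2: effect on a crude ratio when true risk is equal.** Let *s* be the share of complications in the first 3 post-operative months. Assume that the rest are spread evenly up to 14.1 months. For NET follow-up of *T* months:

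apparent NET/control ratio = s + (1 − s) × (T − 3)/(14.1 − 3)

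For example, s = 0.8 and T = 8 give 0.8 + 0.2 × 5/11.1 = 0.89.

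| Share within 3 months | T = 8 | T = 9 | T = 10 |
|---|---|---|---|
| 100% | 1.00 | 1.00 | 1.00 |
| 90% | 0.95 | 0.95 | 0.96 |
| 80% | 0.89 | 0.91 | 0.93 |
| 50% | 0.73 | 0.77 | 0.82 |
| Constant rate throughout (T/14.1) | 0.57 | 0.64 | 0.71 |

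**Step 3: does a surgery-based window fit?** Ninety days is 90/30.4375 = 2.96 months. After the latest on-schedule NET operation (month 7) it ends at about month 10, inside the 15 months. Section 5.2 says that up to three operations should be finished at least three months before the end of the study, so 90 days also fits after expected re-operations.

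**The case against.** The strongest reply is that most surgical complications may well arise early, and that Section 5.2 chose 15 months so that recovery after all surgery would be observed in both arms. If every complication falls within about three months, the unequal tail does no harm. This stands. A reader might infer that delayed surgery is bound to look safer, but the documents give no complication timing and do not support that certainty. Nor do they support a figure in percentage points. Five extra months at an assumed 0.5-1% per month would give 2.5-5 points, but that rate is not in the protocol and could be close to zero.

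A reader might also infer that six scheduled visits against two or three means lost events in NET. That does not follow. A CRF that records everything since surgery, checked against hospital records (source documents under Section 13.1), loses nothing by being completed less often. The schedule in Section 9.2 is not legible enough to show which visits collect complications. The five-month wait for a first visit arises only when NET surgery falls at the month-7 limit; at target timing the first visit comes 2 to 4 weeks after surgery in control and about one month after in NET.

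Randomisation is also a sensible origin for AI side effects, because both arms start the AI then, and those effects share this list. Finally, the SAP may define a post-operative window, and its absence from the protocol is not in itself a fault.

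What these points do not remove is the unequal time at risk. The protocol itself fixes the time origin and the common end at month 15, and its default test makes no allowance for time since surgery. Late events cannot be dismissed on its own account either: Section 5 describes high complication rates after reconstruction and frequent later revision surgery.

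**Conclusion.** The point holds as one of unequal exposure. On the protocol's own dates, control has about 13 to 14.5 months of post-operative observation and NET 8 to 10, a gap of about 5 months at target timing. Any resulting distortion favours NET.

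Its size cannot be fixed from the documents. It is nil if all complications occur within about three months, modest (ratio 0.89-0.93) if 80% do, and material (0.73-0.82) if only half do. These ratios assume equal true risk, an even spread of later events, on-schedule surgery and complete recording of events. The stronger inferences, that bias is built in whatever the timing or that fewer visits alone lose events, are not supported.

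This affects one component of one secondary outcome and not the primary endpoint. It should still be corrected, because this is the trial's comparison of surgical harm and the remedy is cheap.

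**What to change.** Split the timing of outcome 6 in Section 6.2 and the Synopsis. Keep the present list from randomisation for AI side effects. For complications, make the between-arm comparison Clavien-Dindo events within an equal fixed interval from the date of each breast or axillary operation, for example 30 and 90 days. State the interval in Section 11.4 and in the SAP. Take the events from the existing complication CRF and hospital records, dated against the operation, in both arms. Report later events to month 15 descriptively, with the post-operative follow-up time in each arm.

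The cost is a change of outcome wording and of CRF dating. No visit is added and the sample size does not change. The downside is that complications after the window leave the formal comparison, so a true late difference would be seen only descriptively.
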